11.2 Analysis Plans

Thomas Jefferson University Hospital cares for approximately 200 patients with female lower genital tract cancer per year. The patients studied in this project will be women over the age of 18 who have a diagnosis of cervical, vaginal or vulvar cancer. The patient population of this project will reflect the population demographics found at major American urban academic health centers. The overall TJUH demographics include 60 % Caucasian, 16 % African American, 13 % Hispanic, 5 % Asian, 1 % Other, and 5 % unknown patients. The goal of this pilot study is to enroll 40 patients over 2 years. Given that these women have been diagnosed with cancer, they are usually very motivated to participate in research studies that include additional evaluations and, therefore, we do not expect recruitment to be a major issue.

For the primary hypothesis the number of SLN detected by CEUS will be compared to the number of SLN detected by the standard of care (i.e., by blue dye or by PET-CT) using paired t-test or paired Wilcoxon test (depending on whether the data is normal distributed or not).

For the secondary hypothesis the percentage of SLNs with metastatic deposits identified by lymphosonography and by blue dye will be pairwise compared after eliminating the SLNs identified by both methods using two-sample t-test or Wilcoxon test (again after testing for normalcy). The histopathological assessment of the surgically removed LNs will serve as the reference standard.

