2.2.1 Primary Endpoints

The number of SLNs identified by lymphosonography as well as blue dye or PET-CT will be determined for each subject.

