11.1 Study Hypotheses

Primary hypothesis: Does lymphosonography identify more SLNs in patients with cervical, vaginal or vulvar cancer than the standard of care? The fundamental hypothesis is that on average lymphosonography will detect 20% more SLNs than the standard of care.

Secondary hypothesis: Does lymphosonography identify more SLNs with metastatic deposits in patients with cervical, vaginal or vulvar cancer compared to the standard of care? The fundamental hypothesis is that approximately 20% more cancerous SLNs will be detected with CEUS.

H1: On average lymphosonography will detect 20% more SLN than the standard of care (blue dye or PET-CT).

H1₀ The mean number of SLNs per subject identified by lymphosonography is less than 120% of those identified by standard of care.

H1_a The mean number of SLNs per subject identified by lymphosonography is greater than 120% of those identified by standard of care.

H2: On average 20% more cancerous SLNs will be detected by lymphosonography than by standard of care (i.e., blue dye) using pathology as the reference standard.

H2₀ The % of metastatic SLNs identified by lymphosonography is less than 120% of that identified by standard of care.

H2_a The % of metastatic SLNs identified by lymphosonography is greater than 120% of that identified by standard of care.

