11.4 Sample Size Considerations

The sample size analysis is based on the primary aim of this study (i.e., on Aim 1) and assumes that on average lymphosonography will detect 20% more SLN than the standard of care (blue dye or PET-CT]. Hence, a power analysis was performed using NCSS/PASS 2019 (NCSS, East Kaysville, UT) and a sample size of 40 patients achieves 86.9% power to detect the effect size of

0.5 (i.e., assuming the 20% more detected SLN with CEUS versus the standard of care techniques, and twice of standard deviation of paired difference) at 5% significance level using a two-sided paired t-test.

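### Section 11.2 lets an unspecified normality check choose the primary test, and neither of the two candidate tests addresses the 120% ratio of means in H1

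*Combined protocol and SAP*

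**What the plan says.** Section 2.2.1 makes the primary endpoint a per-patient count under each method: "The number of SLNs identified by lymphosonography as well as blue dye or PET-CT will be determined for each subject".

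Section 11.1 states the null as "The mean number of SLNs per subject identified by lymphosonography is less than 120% of those identified by standard of care" and the alternative as "The mean number of SLNs per subject identified by lymphosonography is greater than 120% of those identified by standard of care". The parameter is therefore a ratio of means, with a margin of 1.20.

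Section 11.2 compares the two counts "using paired t-test or paired Wilcoxon test (depending on whether the data is normal distributed or not". It does not name a normality test or a threshold, and does not say whether the check applies to the paired differences or to the raw counts. It contains no factor of 1.2, no ratio or log scale, and no estimate with a confidence interval.

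Section 11.4 reports that "a sample size of 40 patients achieves 86.9% power to detect the effect size of" 0.5, "at 5% significance level using a two-sided paired t-test". The effect size is explained as "assuming the 20% more detected SLN with CEUS versus the standard of care techniques, and twice of standard deviation of paired difference".

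**The concern.** Three sections describe three different things. The hypothesis is about a mean ratio against 1.20, the power is for a t-test of a mean difference against zero, and the analysis is whichever of two tests an unspecified check selects. Two analysts with the same data could run different primary tests and both would be following the plan.

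The signed-rank test addresses the symmetry of the differences about zero. It agrees with a statement about means only if the differences are symmetric. Section 11 makes the comparator blue dye for surgical patients and PET-CT for those receiving chemotherapy, so symmetry cannot be presumed.

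The t-test branch does concern a mean, but it asks whether the mean difference is zero. A significant result from either branch could be reported as support for a 20% gain that has not been tested.

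**Working it through.** **1. The stated power.** Inputs from Section 11.4: n = 40, effect size 0.5, two-sided 5%, paired t-test. Noncentrality = 0.5 × √40 = 3.162 on 39 degrees of freedom. Power from the noncentral t distribution is 86.94%, which reproduces the stated 86.9%.

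**2. What that power refers to.** Let M be the standard-of-care mean. A 20% gain is a difference of 0.2M. An effect size of 0.5 means that the SD of the difference is twice the difference, so 0.4M. The test is against zero: 0.2M / 0.4M = 0.5. But a gain of exactly 20% is a true ratio of 1.20M / M = 1.20, the boundary of the null in Section 11.1. At that boundary the planned t-test rejects in about 87% of trials, where an upper-tail test of the 1.20 margin would reject in 2.5%. Rejecting zero difference is correct in itself. The error lies in reading it as evidence for the alternative in H1.

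**3. Power against the margin.** Test the mean of CEUS − 1.2 × SOC, upper tail 2.5%, n = 40. Assume that its SD is also 0.4M. The standardised effect is (true ratio − 1.20) / 0.4.

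| True ratio | Standardised effect | Power |
|---|---|---|
| 1.20 | 0 | 2.5% |
| 1.25 | 0.125 | 11.7% |
| 1.30 | 0.25 | 33.8% |
| 1.40 | 0.5 | 86.9% |

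**4. Which branch would be used.** The documents give no SLN mean for this population. Section 1.1 quotes breast-cancer figures from 1.67 to 3.2 nodes per patient. Taken as an assumed range for M, these give an SD of 0.4 × 1.67 = 0.67 to 0.4 × 3.2 = 1.28. Simulated normal differences rounded to integers, n = 40, normality tested at 5%:

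| SD of difference | Shapiro-Wilk rejects |
|---|---|
| 0.67 to 0.8 | 100% |
| 1.0 | 99.8% |
| 1.28 | 87% |
| 1.5 | 64% |
| 2 | 28% |
| 3 | 12% |

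For SDs of 0.67 to 1.28, Lilliefors rejects in 99-100% and D'Agostino's moment-based test in only 5-7%. With Poisson counts, Shapiro-Wilk rejects in 9-69% if the methods are independent (means 5 down to 1), and in 39-100% if 70% of nodes are shared. The Poisson runs used 250 replicates, so these rates are good to about ±6 points.

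**5. What the Wilcoxon branch does when selected.** All shapes here are assumptions.

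- *Near-symmetric differences:* the two tests disagree in at most 5% of trials. In the rounded-normal runs both have power of about 83-86%.
- *Skewed, mean exactly zero:* differences of −1 (60%), 0 (25%) and +4 (15%) have mean −0.60 + 0.60 = 0. Signed-rank rejects in 37% and the t-test in 6%. Differences of +1 (50%), 0 (40%) and −5 (10%) have mean 0.50 − 0.50 = 0. The rates are 50% and 9%.
- *Skewed, ratio below 1:* CEUS/SOC pairs of 3/2 (50%), 2/2 (35%) and 0/4 (15%) have means of 2.2 and 2.3, a ratio of 0.96. Signed-rank favours CEUS in 22% of trials and the t-test in 3%.
- *Mixed comparator at ratio 1.20, testing CEUS − 1.2 × SOC:* half the patients have zero-inflated PET-CT counts (50-70% zeros, mean 4-5 nodes otherwise). The two-stage rule rejects in the upper tail in about 4-10% of trials against 2.5%. In one set of these runs the t-test alone gave 2.6-4.4%. Shapiro-Wilk rejected in 17-68%.

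**The case against.** This is a single-site pilot. Conditional t-test/Wilcoxon wording is common, and both options are declared in advance. For near-symmetric differences the choice barely changes the result. The documents give no SLN mean, SD or PET-CT zero rate for this population, so every skewed example above rests on an assumed shape. All of this stands, and it limits the size of the point. It does not remove it: the plan states a formal hypothesis and a power, and has no data to show that it is in the benign case.

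A reader might infer that integer counts at n = 40 will almost always be sent to Wilcoxon. The documents do not support that. No normality test is named, and the rejection rate falls quickly with a larger SD or a moment-based test.

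A reader might also infer a severe loss of power from the switch. If the extra CEUS nodes cluster in a few patients, signed-rank has about 9% power against about 56% for the t-test at a true ratio of 1.4. That holds only on CEUS − 1.2 × SOC, which Section 11.2 does not use. On the planned zero-difference comparison both tests reach about 100% in that scenario. The figures also move with the assumed mean: raising it from 1.67 to 2.0 gives 31% against 69%.

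Finally, it can be said that the missing margin, not the switch, is the main fault. That is right, and deleting the switch alone would leave it in place.

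**Conclusion.** The point holds in two parts.

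The larger part follows from the text and the plan's own inputs, and needs no assumed distribution of counts. Neither branch tests H1, because both compare with zero. With the SD read as twice the difference, the powered test rejects in about 87% of trials at the boundary of the null.

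The smaller part is the normality switch. It leaves the primary test undetermined until the data are seen, and one option does not test a mean under skewness. Wilcoxon would often be selected: in 87-100% of trials with Shapiro-Wilk and an SD of the difference of about 0.7-1.3 nodes. The consequence ranges from almost nothing to an upper-tail error of about 4-10% against 2.5%, the latter only if zero-inflated PET-CT counts are assumed and the 1.2 margin is tested. A higher error rate for the planned analysis cannot be claimed from these documents.

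**What to change.** In Section 11.2, delete the normality switch and pre-specify one test of the mean for H1, whatever the shape of the data:

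- if the 120% margin is kept, a one-sample t-test on CEUS − 1.2 × SOC for each patient;
- if H1 is restated as any increase, a one-sample t-test on CEUS − SOC, with Section 11.1 reworded to match.

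In either case, report the ratio of means with a patient-level bootstrap 95% confidence interval, and keep the Wilcoxon test as a labelled sensitivity analysis.

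If the margin is kept, restate the power in Section 11.4 with its assumed true ratio and SD. The 86.9% belongs to a test against zero difference. It does not describe a true ratio of 1.20 tested against a margin of 1.20. If H1 becomes any increase, the 86.9% stands on its stated assumptions.

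The cost is a few sentences in Sections 11.1, 11.2 and 11.4, with no new data. There are two downsides. The t-test is more sensitive to a single outlying patient, which the bootstrap interval and the sensitivity analysis should reveal. And with the margin kept, the restated power is less favourable.

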1.2 Rationale for the Proposed Study

Women with cervical, vaginal or vulvar cancers will undergo surgical resection and/or chemotherapy and/or radiotherapy of their cancer (depending on their staging). The SLN mapping for this group of patients is done as part of the staging process using PET-CT, for patients with stage I that undergo surgical resection there is an additional SLN mapping procedure performed using blue dye. The standard of care for the surgical group of patients is LN dissection usually bilateral given the midline anatomical location of the female lower genital tract. Patients with tumors of higher stages that undergo chemotherapy and/or radiotherapy undergo systematic PET-CT for the continuing SLN staging during treatment. However, each of these methods has potential limitations that can impact the detection of SLNs and the accuracy of disease staging. Our group has demonstrated that CEUS after subdermal administration of a tissue-specific ultrasound contrast agent such as Sonazoid, can be used to noninvasively map lymphatic drainage and localize SLNs (so called "lymphsonography"). Our NIH funded investigations using the Sinclair swine model with naturally occurring melanomas have confirmed that CEUS is superior to radioisotope imaging; detecting almost 20 % more SLNs.

The fundamental hypothesis of this project is that lymphosonography can be used to identify SLNs in patients with cervical, vaginal or vulvar cancers with better success rates than the standard of care. In summary, this study aims to determine the clinical potential of lymphosonography for noninvasive SLN mapping via subdermal injection of tissue-specific UCA in 40 patients with cervical, vaginal or vulvar cancer and compare the use of lymphosonography to the standard of care.

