2.1.2 Primary Objectives

The primary objectives of this trial are:

1. To determine the concordance between lymphosonography and the standard of care in the identification SLNs in patients with cervical, vaginal or vulvar cancer.
2. To determine if lymphosonography can identify more SLNs with metastatic deposits in patients with cervical, vaginal or vulvar cancer when compared to the standard of care.

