8.5 Halting Rules

The whole trial may be discontinued at the discretion of the PI or the sponsor in the event of any of the following:

- Occurrence of AEs unknown to date in respect of their nature, severity and duration
- Medical or ethical reasons affecting the continued performance of the trial

9 Study Oversight

In addition to the PI's responsibility for oversight, study oversight will be under the direction of the SKCC's Data and Safety Monitoring Committee (DSMC). The SKCC DSMC operates in compliance with a Data and Safety Monitoring Plan (DSMP) that is approved by the NCI.

10 Clinical Site Monitoring and Auditing

Clinical site monitoring and auditing is conducted to ensure that the rights of human participants are protected, that the study is implemented in accordance with the protocol and/or other operating procedures, and that the quality and integrity of study data and data collection methods are maintained. Monitoring and auditing for this study will be performed in accordance with the SKCC's Data and Safety Monitoring Plan (DSMP) developed by the SKCC Data and Safety Monitoring Committee (DSMC). The DSMP specifies the frequency of monitoring, monitoring procedures, the level of clinical site monitoring activities (e.g., the percentage of participant data to be reviewed), and the distribution of monitoring reports. Some monitoring activities may be performed remotely, while others will take place at the study site(s). Appropriate staff will conduct monitoring activities and provide reports of the findings and associated action items in accordance with the details described in the SKCC DSMP.

11 Statistical Considerations

The fundamental hypothesis of this project is that lymphosonography can be used to identify SLNs in patients with cervical, vaginal or vulvar cancers with greater success than the standard of care. For this project the standard of care is either blue dye injections (if the subject goes to surgery) or PET-CT results (if the subject goes to chemotherapy) as part of their management.

In this study we do not focus on whether an SLN is correctly identified, as there is no way of knowing that (unless the subject goes for surgery and the SLN has metastatic deposits but this will only be the case for a small subset) and the number of SLNs not identified by lymphosonography or by the standard of care will, for obvious reasons, be unknown. Hence, we presume all identified SLN are correctly identified.

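### H2 asks whether lymphosonography finds more than 120% of the metastatic SLNs found by blue dye, but the planned analysis drops the shared nodes and tests no 1.2 margin, so it cannot answer

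*Combined protocol and SAP*

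**What the plan says.** Section 11.1 states H2 in two forms. The heading line is about numbers of nodes: "20% more cancerous SLNs will be detected by lymphosonography than by standard of care (i.e., blue dye) using pathology" as the reference standard. The formal alternative is about a percentage: "The % of metastatic SLNs identified by lymphosonography is greater than 120% of that identified by standard of care". Neither form says what the percentage is a percentage of.

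Section 11.2 gives the only H2 analysis. The percentages for lymphosonography and blue dye are to be "pairwise compared after eliminating the SLNs identified by both methods using two-sample t-test or Wilcoxon test", after a check of normality. It adds: "The histopathological assessment of the surgically removed LNs will serve as the reference standard". The sentence calls the comparison both pairwise and two-sample, whereas the sentence before it names paired tests for H1. No 1.2 factor appears, the unit of analysis (node or patient) is not given, and no other section analyses H2 on all nodes.

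On the population, section 1.2 says that "for patients with stage I that undergo surgical resection there is an additional SLN mapping procedure performed using blue dye". The opening of section 11 says correct identification cannot be known "unless the subject goes for surgery and the SLN has metastatic deposits but this will only be the case for a small subset", and that "the number of SLNs not identified by lymphosonography or by the standard of care will, for obvious reasons, be unknown". Section 11.1 and the Study Summary treat the metastatic-node question as secondary. Section 2.1.2 lists it among the primary objectives: "To determine if lymphosonography can identify more SLNs with metastatic deposits in patients with cervical, vaginal or vulvar cancer".

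**The concern.** A claim of 20% more is a statement about a ratio of two totals, and nodes found by both methods belong in both totals. Removing them keeps the difference between the methods but loses the base against which 20% is measured. Discarding concordant findings is sound for a McNemar-type test of whether the two methods differ at all. H2 is not that hypothesis, and section 11.2 does not name that test.

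Followed as written, the analysis would give a p-value for equality of two undefined percentages. A report could present it as evidence for or against the 120% claim although it bears on neither. On one reading of the percentage it could also show no difference, or favour blue dye, when lymphosonography alone found more metastatic nodes.

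**Working it through.** **Inputs.** The threshold of 1.2 is from section 11.1; the elimination step and the tests are from section 11.2. The documents give no node counts, metastatic rates or sample size for H2, so every count below is an assumption. The one power figure, 86.9% in section 11.4, concerns H1. It reproduces (two-sided paired t-test, n=40, effect size 0.5, noncentrality 0.5 × √40 = 3.16: 86.94%) and is not affected.

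**1. The ratio is lost.** Let s, b and c be the metastatic nodes found by both methods, by CEUS only and by dye only.

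- H2 ratio = (s+b)/(s+c).
- The ratio exceeds 1.2 exactly when b − 1.2c − 0.2s > 0, that is, when s < (b − 1.2c)/0.2.

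Elimination deletes the 0.2s term.

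| b, c | Ratio at different s | Ratio is 1.2 at s = |
|---|---|---|
| 9, 1 | s=0: 9.0; 10: 1.73; 39: 1.20; 100: 1.08 | (9 − 1.2)/0.2 = 39 |
| 6, 3 | s=0: 2.00; 6: 1.33; 12: 1.20; 20: 1.13 | (6 − 3.6)/0.2 = 12 |
| 2, 1 | s=3: 5/4 = 1.25; s=5: 7/6 = 1.17 | (2 − 1.2)/0.2 = 4 |

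Within each row the retained data are identical. Whenever b > 1.2c, a small s satisfies the alternative and a large s satisfies the null. When b ≤ 1.2c the ratio cannot exceed 1.2 at any s. The retained counts can therefore sometimes rule H2 out but can never establish it.

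**2. Direction depends on what the percentage means.**

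*Positivity among each method's remaining nodes:*

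- Masking: CEUS-only 9/45 and dye-only 1/5 are both 20% (p=1.0), although CEUS alone found nine metastatic nodes and dye alone one.
- Reversal: CEUS-only 6/30 (20%) against dye-only 3/6 (50%) favours dye (t-test p=0.13), although CEUS alone found twice as many.
- Simulation with 20 surgical patients, 1.5 shared, 1.5 CEUS-only and 0.5 dye-only nodes per patient, all 20% metastatic. The true ratio is (0.3+0.3)/(0.3+0.1) = 1.50. Among runs in which CEUS found more metastatic nodes, the planned percentages favoured dye in 41%.
- If H2 itself means positivity, elimination still changes it. With shared 12/12, CEUS-only 2/10 and dye-only 6/24, all nodes give 14/22 = 63.6% against 18/36 = 50.0% (ratio 1.27). The remainder gives 20% against 25% (ratio 0.80). The count ratio is 14/18 = 0.78, so the two readings of H2 disagree and one must be chosen.

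*Each method's share of the metastatic nodes:* after elimination the comparison is b/(b+c) against c/(b+c). For b=6 and c=3 that is 67% against 33% at every s. The pooled direction is right, but the ratio is always b/c = 2, whatever the H2 ratio is. Averaging the shares per patient can still reverse: three patients with (b, c) of (4,0), (0,1) and (0,1) give mean shares of 33% and 67% on counts of 4 and 2.

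**3. The two-sample test.** In simulations under the positivity reading (10 to 20 patients, within-patient correlation 0 to 0.5), type I error at an assumed 5% level was 4.2% to 5.4% for the t-test and 3.3% to 5.2% for the rank-sum test. Only under the share reading is it inflated, to about 17% asymptotically: P(|Z| > 1.96 × √0.5).

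**The case against.** The strongest reply is that the percentage can be read throughout as the share of pathology-positive nodes that each method found. The two statements of H2 then agree, because a common denominator makes the ratio of percentages equal to the ratio of counts, and dropping shared nodes keeps the pooled direction. This stands against any flat claim that the analysis points the wrong way. It does not rescue the 1.2 ratio, which elimination destroys on this reading too.

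Second, large examples do not fit this trial. Section 1.1 cites 3.2 SLNs per patient with this agent in breast cancer. At that yield, b=9 with s=39 means 48 metastatic nodes found by CEUS, or 48/3.2 = 15 patients with every node positive. That is fair, but the algebra needs no large counts: with b=2 and c=1 the answer turns on whether three or five nodes were shared.

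Third, a reader might infer that the unpaired test is itself the reason H2 fails. The documents do not support that. Once shared nodes are removed the two node sets are disjoint, Wilcoxon alone could mean either version, and error rates under the positivity reading are near nominal. The inflation and the pooled reversal also belong to different readings and cannot be charged together. What remains is a wording conflict between pairwise and two-sample.

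Fourth, the stakes are modest, and the ratio could still be reported descriptively if each node is recorded by method. That is so, but the plan does not say it will be.

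**Conclusion.** The concern holds in a limited form. Section 11.2 cannot deliver the H2 comparison in section 11.1 because shared nodes are removed, the percentage is undefined and no 1.2 margin is tested. This is algebra and holds for any node counts with b > 1.2c. Masking or reversal of the count result is a possibility under the positivity reading, not a general property of the plan. Its frequency (41% in the simulated setting) rests on assumed rates.

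A reader might go further and conclude that H2 would produce false positives or would systematically favour blue dye. The documents settle neither the denominator nor the unit, so neither conclusion follows.

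Severity is minor to should-fix. H2 is a secondary aim of a pilot sized on Aim 1 only, in a surgical subset described as small, although section 2.1.2 places it under the primary objectives.

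**What to change.** In section 11.2:

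1. Delete the elimination step. Define H2 on counts of pathology-confirmed metastatic SLNs in surgical patients whose nodes were removed and examined, with shared nodes in both counts.
2. Make the main result the per-patient mean of (CEUS − 1.2 × blue dye metastatic SLNs), with a patient-level 95% CI read against 0. It is defined even when the dye count is zero.
3. Report s, b, c and the ratio (s+b)/(s+c) descriptively.
4. Drop the two-sample test, which also removes the pairwise/two-sample conflict. Do not add a separate equality test: a sign-flip test rejected in only 0% to 2% of simulated runs and does not address 1.2.
5. Label H2 as estimation in a small subset, and give it the same status in sections 2.1.2 and 11.1.

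The difference is preferred to a bootstrap CI for the ratio on simulated grounds (8, 12 or 20 patients, true ratio 1.2, low assumed node rates). Coverage was 84% to 93% for the difference and 48% to 92% for the ratio. At least one resample had a zero dye count in 34% of trials in the best of six settings and in 75% to 99% in the other five.

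The cost is SAP wording and a few lines of code. No new data are needed if each node is logged as CEUS-only, dye-only or both. The downside is wide intervals with approximate coverage. In the 1.50-ratio setting above, the lower limit of a 95% t-interval exceeded 0 in 4%, 10% and 19% of runs with 10, 20 and 40 surgical patients, so H2 will probably stay inconclusive.
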